At eight months post intervention (**T3** - six months postpartum at the six-month well baby visit), all women will once again be contacted and complete all measures (including weights taken on available pediatric clinic adult scales –same model as prenatal scales). Participants will receive \$50.00 for their participation. Outcome data from charts will be collected by team members blind to group assignment.

If study visits cannot be conducted face-to-face, data will be collected through telehealth methods such as via phone or video call (Zoom or Facetime etc.).

**Sampling.** Women will be recruited from the antenatal clinic if they are: between 18 and 40 years old, in their first trimester with an uncomplicated singleton pregnancy of less than 19 weeks, and self-identify as either Black or Hispanic and can read and speak English or Spanish. A completed sample size of 182 Black and Hispanic women from JMC in the Bronx and 182 Black and Hispanic women from OSU Total Health and Wellness clinics will be required to meet the determined sample size of 364 total (at 4 data collection points for each, resulting in ~1,450 observations). This will have greater than 80% power to detect small to moderate effects (i.e. 25 or greater) between group differences in healthy lifestyle behaviors, psychosocial health, and outcomes testing at alpha = .05 for all proposed models. The sample of 364 will have > .80 to detect a small to medium mediated effect. The sample of 364 will have > .80 to detect a small to medium mediated effect.

**Setting. Jacobi Medical Center** is part of New York City Health + Hospitals (NYC H + H), the largest municipal hospital system in the United States. New York City Health + Hospitals oversees the public health care system in all the five boroughs that comprise New York City. It provides one-fifth of the total number of discharges and more than one-third of the emergency services and hospital-based clinic visits in all of New York City. Jacobi Medical Center is an academic affiliate of the Albert Einstein College of Medicine. Jacobi Medical Center is located in the Bronx. As one of the largest health care delivery facilities in the Bronx and in New York City, Jacobi Medical Center has developed a world- wide reputation of distinction. It is renowned for its primacy in

07/30/2021

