### **Analysis plan.**

**Data management:** Survey data will be obtained using paper and pencil surveys and at each site all surveys will be scanned using Remark software to ensure accuracy and avoid the necessity of double data entry. Fitbit data will be uploaded using Bluetooth technology at each data point (with T0 baseline data being collected between screening and the first group prenatal care session) and entered into an Excel database. Data from the 24 hour diet recalls will be manually entered at each site into Food Processor and then exported into an Excel file for data analyses. At each visit, weights will be recorded. Obstetrical chart data will be extracted at each site. [name] will merge the Ohio and New York data files, perform data cleaning, construct analytic variables, assess psychometrics and conduct both interim and final analyses.

**Data Analysis:** Preliminary analyses: Statistical analyses of these data must not only demonstrate the efficacy

07/30/2021

of the COPE-P intervention, but also map the trajectories of group differences over time, and identify subgroup differences. Analysis will begin with characterization of the sample with descriptive statistics that identify differences between the COPE-P and PregnancyPlus groups 1) evident at baseline, despite randomization and 2) between groups due to differential attrition. Data will be screened for normality, outliers, and homogeneity. Appropriate nonparametric analyses will be considered in situations of irresolvable heterogeneity. We will evaluate the psychometric qualities (reliability, convergent and discriminant validity) of the scales, employing both exploratory factor analyses and SEM measurement models. Descriptive statistics will be used to summarize the sample characteristics and distribution of each variable. Missing Data. All data analyses will be completed as intention to treat analyses (i.e., individuals analyzed by group according to original random assignment, without regard to adherence to the intervention). Missing data will be imputed, when appropriate, using multiple imputation in SAS v9.4 PROC MI.

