For all continuous outcomes, such as anxiety, the basic model, to which we can add our controls and predictors. The level 1 submodel estimates how each participant's anxiety changes over the four data collection periods. The level 2 submodel will relate the inter-individual differences to intervention group and other time-invariant predictors and controls, such as medication (i.e., antidepressants) and have begun therapy (i.e., in usual care for mental health diagnoses), and will estimate a participant's initial anxiety level and rate of change in anxiety. Anxiety will be modeled in terms of random subject effects (intercept and time trends) to account for individual differences in how participants change over time. We will begin with a linear model for time but will investigate nonlinear effects as suggested by the data. Subsequent models will contain time-varying covariates (i.e., dose of intervention, weight, exercise) and thus will focus on within-participants effects, that is, whether within-participant differences in the covariates are associated with within-participant differences in anxiety. We will examine the potential of cognitive beliefs and perceived difficulty in leading a healthy lifestyle in mediating the effects of the COPE-P program on healthy lifestyle behaviors and psychological symptoms. Rather than detecting mediated effects with the causal steps approach of Baron and Kenny, we will use the Joint Significance Test established by MacKinnon, which assesses the statistical significance of the X to M relation,  $\alpha$  path, and then the M to Y relation,  $\beta$  path. If both are statistically significant, there is evidence of mediation. Models with more than one mediator are simply extensions of the single-mediator case. In our multilevel models, we will investigate mediation effects within the different levels of analysis and across levels. Finally, we will explore characteristics that may moderate healthy lifestyle behaviors, psychosocial health, and birth outcomes (e.g., race/ethnicity, age, parity, language spoken, level of education, income, marital status) in the above models. The proposed examination of mediators and moderators should allow for increased understanding of mechanisms underlying any intervention effect and different responses among the participants. The most appropriate covariance structure for the residuals  $\epsilon_{ij}$  will be determined after data collection and the correlation of responses over time is estimated. Several covariance structures will be examined and the resulting models compared for fit using the quasi-likelihood independence model information criterion (QIC) fit using SAS 9.4 (Proc MIXED).

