
Should any of the outcomes need to be dichotomized (i.e., present vs. absent), we will fit a multi-level random effects logistic regression models with time-varying covariates. The basic model, to which we will add our controls and predictors, can be written: where  $i$  indexes participants,  $t$  indexes time, COPE-P is an indicator of the intervention group, COPE-P x Time is the intervention by time interaction,  $X_k$  is a set of time-varying covariates measured for each participant  $i$  at time  $t$  and  $u_i$  is participant-specific error term. The interaction term COPE-P x Time is the test of the effectiveness of the COPE-P program. If successful, the regression coefficient will be negative, indicating that the modeled probability of psychological symptoms declined more

07/30/2021

rapidly with time in the COPE-P group than they did in the PregnancyPlus group. We will fit these models using SAS 9.4 (Proc NLMIXED).

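### Adding weight and exercise as time-varying covariates does not by itself give within-participant effects; each must be split into a woman's mean and her deviation from it

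*Combined protocol and SAP*

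**What the plan says.** The relevant text is the paragraph on continuous outcomes under Hypothesis-driven analyses in the Analysis plan.

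- **Model.** "Anxiety will be modeled in terms of random subject effects (intercept and time trends) to account for individual differences". The level 1 part covers four occasions: "The level 1 submodel estimates how each participant's anxiety changes over the four data collection periods".
- **Covariates.** A later set of models adds dose, weight and exercise: "Subsequent models will contain time-varying covariates (i.e., dose of intervention, weight, exercise) and thus will focus on within-participants effects".
- **Target.** The question for those models is "whether within-participant differences in the covariates are associated with within-participant differences in anxiety".
- **Time.** "We will begin with a linear model for time", and the same sentence goes on to allow nonlinear terms if the data suggest them.

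No person mean, deviation score or participant fixed effect is described for these covariates. In the model for dichotomised outcomes, the covariate set "is a set of time-varying covariates measured for each participant" at each time, again with no split. The only mention of separating levels concerns mediation, and it gives no method. Data management confirms that weight is repeated: "At each visit, weights will be recorded". Fitbit data are uploaded at each data point.

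**The concern.** The plan treats the presence of a time-varying covariate as the reason why the effect is within-participant. A random-effects model does not work that way. Weight at a visit carries two kinds of information: how heavy this woman is compared with others, and how far she is from her own usual weight. One coefficient for the undivided value has to serve both.

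At stake is a sentence in the eventual report. It could say that a woman's anxiety moves with her weight or activity, when the data show only that heavier or less active women differ from others. It could also miss or reverse a real within-woman relation.

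Time raises a second, smaller issue. Weight is expected to peak at T1 (about 31 weeks) and to be lower at the postpartum visits. Women enter by scoring at or above a cut-off on one of three symptom scales, and those screening scores serve as baseline, so some fall from T0 to T1 may be expected in both arms. If time is kept linear, even a deviation score for weight can pick up this shared pattern.

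Dose of intervention is not part of this point.

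**Working it through.** **Inputs from the documents.** Four occasions (T = 4) and a "sample size of 364 total (at 4 data collection points for each, resulting in ~1,450 observations". Check: 364 × 4 = 1,456, which agrees. The documents give no figure for the covariate effects, and no SDs or outcome correlation. Everything below that needs those is assumed.

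**Assumed inputs.** Outcome random intercept SD 3.3, random slope SD 0.6 per visit, residual SD 3.5 (GAD-7 points). Between- and within-woman SD: weight 18 and 5 kg; steps 2.5 and 2.0 thousand per day.

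**Formula.** Let β_B be the effect of a woman's long-run level and β_W the effect of her deviation from it. With a random intercept, the undivided covariate has expected coefficient (1 − w)β_W + wβ_B, where

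w = ψTσ_B² / [ψ(Tσ_B² + σ_W²) + (T − 1)σ_W²], and ψ = (1 − r)/(1 + (T − 1)r).

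Here r is the outcome's residual intraclass correlation.

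- r = 3.3²/(3.3² + 3.5²) = 10.89/23.14 = 0.47, so ψ = 12.25/(12.25 + 4 × 10.89) = 0.2195.
- Weight: 0.2195 × 1,296 / (0.2195 × 1,321 + 75) = 284.5/365.0 = **0.78**.
- Steps: 0.2195 × 25 / (0.2195 × 29 + 12) = 5.49/18.37 = **0.30**.

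The random slope changes these by less than 0.01. If β_B is defined on the observed four-visit mean instead of the long-run level, the shares are 0.79 and 0.35.

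**Range.** Between-woman share w by r and by the covariate's between-woman share of variance (ICC; 324/349 = 0.93 for the weight assumption, 6.25/10.25 = 0.61 for steps):

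| Covariate ICC | r = 0.3 | r = 0.5 | r = 0.7 |
|---|---|---|---|
| 0.5 | 0.30 | 0.20 | 0.11 |
| 0.7 | 0.51 | 0.37 | 0.23 |
| 0.9 | 0.80 | 0.69 | 0.53 |

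**False-positive rates.** Simulation of 364 women at 4 visits, generalised least squares with the variances above, true β_W = 0, two-sided 0.05. Ranges are across repeat runs.

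| Covariate (SD between/within) | Assumed β_B | Undivided | Deviation term |
|---|---|---|---|
| Weight 18/5 | 0.05 per kg | 96–98% | 4–5% |
| Weight 18/5 | 0.025 per kg | 53–55% | 4–5% |
| Weight 16/7 | 0.05 per kg | 85–88% | 5–6% |
| Steps 2.5/2.0 | −0.4 per thousand | 75–78% | 4–5% |
| Steps 2.5/2.0 | −0.2 per thousand | 28% | 5% |

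**When the effects are not zero.** Covariate and outcome standardised, r = 0.5. With β_W = −0.2 and β_B = +0.2, the undivided coefficient was +0.075 at ICC 0.9 (sign reversed) and −0.120 at ICC 0.5 (right sign, attenuated). With both effects 0.2, it was 0.20 at both ICCs, so there was no error.

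**Time.** Assumed +8 kg at T1, mean scores 12, 9, 8.5, 8, and no true weight effect. The deviation term was falsely significant in 97–100% of trials under linear time, in 18–50% with a quadratic (depending on the assumed weight profile), and in 3–8% with visit as a factor or an equivalent cubic. With a smaller fall (12, 11, 10.5, 10.5), the linear-time rate was 21%. With a nearly linear decline there was no inflation.

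**The case against.** The best defence has four parts.

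- **Undivided entry is inferred from silence.** The model equations do not appear in the text as read, the stated target is compatible with deviation scores, and data management allows for analytic variables to be constructed. This is fair as far as it goes. If the equations show a split, the point closes. But the plan gives covariate entry itself as the reason for the within-participant reading, and that reasoning is wrong as written.
- **Bias needs the two effects to differ.** This stands. Every false-positive rate above sets the within-woman effect to zero and assumes a between-woman slope. However, nothing in the plan checks whether the effects are equal.
- **The plan does not commit to linear time.** This also stands. Nonlinear terms are allowed, and curvature as large as the assumed 12, 9, 8.5, 8 would probably be detected. The figures for linear time therefore describe a model that the plan may well abandon. What remains is that a quadratic may leave some bias, and that a data-driven choice is less secure than fixing visit as a factor beforehand.
- **These are subsequent models that serve no stated hypothesis.** Correct, and it limits the consequence to the interpretation of the covariates.

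A reader might infer that differences between women dominate both coefficients. The documents cannot show that. It is plausible for weight. For steps, the assumed inputs leave about 70% of the weight within-woman.

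**Conclusion.** The point holds as a wrong inference rule with an inexpensive repair. In the stated model, including weight or exercise does not isolate within-participant effects. The undivided coefficient can be biased for the plan's own target whenever between-woman and within-woman effects differ. Under the assumed variances, the between-woman share is large for weight (about 78%) and smaller but not negligible for steps (about 30%). Even a 30% share gave frequent false positives under the larger assumed slope. All SDs, slopes, correlations and mean profiles are assumptions.

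Three stronger readings are not supported:

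- That the reported conclusion would be wrong. It could be wrong; with equal effects it would not be.
- That the error spreads to the mediation and moderation analyses. The mediators are beliefs and perceived difficulty, and the listed moderators are characteristics such as ethnicity, parity and education. Nothing here shows an effect on either analysis.
- That the test of COPE-P is compromised. For continuous outcomes the basic model precedes these covariate models and is not affected.

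**What to change.** In the subsequent models for continuous outcomes, replace each of weight and exercise by two terms: the woman's own mean over her visits (level 2) and her deviation from that mean at each visit (level 1). State that the within-participant conclusion is drawn from the deviation term only.

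As a secondary safeguard, enter visit (T0 to T3) as a factor with its arm interaction in these models, and do not rely on the linear starting model.

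Suggested sentence: *Weight and exercise will each enter as the participant's mean and her visit-specific deviation from it, with visit as a factor and its interaction with arm; only the deviation coefficient will be interpreted as a within-participant association.*

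The cost is two derived variables per covariate, a few degrees of freedom and this sentence. No new data are needed.
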